9.2 Operational definitions for (S)AEs

Investigators who are clinically qualified at consultant level will be responsible for the detection and documentation of events meeting the criteria and definitions detailed above. For this trial this will be [name].

The Chief Investigator and the clinical team will make decisions as to whether any such events are unexpected in terms of timing or severity and considered related to the study drug, with advice from the DMC as necessary.

All AEs and SAEs will be recorded from the time of study entry until the end of the last study visit.

Depending on severity, when an AE/SAE occurs, the Investigator will review any documentation (e.g. hospital notes, laboratory and diagnostic reports) related to the event and record all relevant information in the CRF and on the AE or SAE form.

Information to be collected will include dose of any medication, type of event, onset date, Investigator assessment of severity and causality, date of resolution as well as treatment required, investigations needed and outcome.

The Investigator will make an assessment of whether the AE/SAE is likely to be related to treatment according to the following definitions:

Unrelated: where an event is not considered to be related to the study drug.

Possibly: although a relationship to the study drug cannot be completely ruled out, the nature of the event, the underlying disease, concomitant medication or temporal relationship make other explanations possible.

Probably: the temporal relationship and absence of a more likely explanation suggest the event could be related to the study drug.

Definitely: The known effects of the study drug or its therapeutic class, or based on challenge testing, suggest that study drug is the most likely cause.

All AEs/SAEs judged as having a reasonable suspected causal relationship (e.g. possibly, probably, definitely) to the study drug will be considered as ARs/SARs. All AEs/SAEs judged as being related (e.g. possibly, probably, definitely) to an interaction between the study drug and another drug will also be considered to be AR/SAR.

To help determine the expected nature of SAEs, appropriate Reference Safety Information (RSI) is provided in the SmPC.

The Investigators will make an assessment of severity for each AE/SAE and record this on the CRF according to one of the following categories:

Mild: an event that is easily tolerated by the participant, causing minimal discomfort and not interfering with every day activities.

Moderate: an event that is sufficiently discomforting to interfere with normal everyday activities.

Severe: an event that prevents normal everyday activities.

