Internal ref. no. (or short title)	MIDNIGHT Trial				
Clinical Phase	Phase 2				
Trial Design	Randomised, double blind, pla	acebo controlled, cross over			
Trial Participants	Intensive care unit medical ar	nd nursing staff			
Planned Sample Size	32				
Treatment duration	3 nights x 2 occasions				
Follow up duration	End of final study visit				
Planned Trial Period	3 years				
	Objectives Outcome Measures				
Primary	To determine the feasibility of a trial of Circadin vs placebo in medical and nursing staff working nightshifts on the intensive care unit.	Recruitment and randomisation of 25 individuals completing both arms of the crossover design.			
Secondary	Determine effect of night shift working on transcriptome.	Differential gene expression between baseline and end of shift on Day 1, and end of shifts series on Day 4.			
	Determine effect of Circadin on transcriptome.	Differential gene expression between placebo and active arms on Day 4.			
	Determine effect of night shift working on cytokine profile.	Serum IL-6 and TNF α levels at baseline, end of shift on Day 1 and on Day 4.			
	Determine effect of Circadin on cytokine profile	Serum IL-6 and TNF α levels after placebo and active arms on Day 4.			
	Determine metabolism of Circadin	Serum melatonin and 6- hydroxymelatonin sulphate levels at each time point			
	Determine effect of Circadin on sleep measures	Verran and Snyder-Halpern sleep scale, Epworth sleepiness scale, data from wristband activity monitor			

	Determine effect of Circadin on psychomotor function Determine whether usual sleep habits impact on effect of Circadin	Psychomotor vigilance task, double digit addition test. Usual sleep habits and owl- lark questionnaires.		
	trial.	focus group.		
Intervention	Circadin [™] or matching placebo			
Formulation, Dose, Route of Administration	Oral, 6mg, modified release tablets			

FUNDING AND SUPPORT IN KIND

FUNDER(S) (Names and contact details of ALL organisations providing funding and/or support in kind for this trial)	FINANCIAL AND NON FINANCIAL SUPPORT GIVEN
British Journal of Anaesthesia/Royal College of Anaesthetists	Financial support for the study.
Flynn Pharma	Provision of Circadin and matching placebo, free of charge.

ROLE OF STUDY SPONSOR AND FUNDER

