9.3 Recording and reporting of SAEs AND SUSARs

All SAEs / SUSARs occurring from the time of written informed consent until 14 days post cessation of trial treatment will be recorded on the SAE / SUSAR report form and faxed to the Sponsor within 24 hours of the research staff becoming aware of the event. Once all resulting queries have been resolved, the Sponsor will request the original form should also be posted to the Sponsor and a copy to be retained on site.

For each SAEs / SUSARs the following information will be collected:

- full details in medical terms and case description
- event duration (start and end dates, if applicable)
- action taken
- outcome
- seriousness criteria
- causality (i.e. relatedness to trial drug / investigation), in the opinion of the investigator
- whether the event would be considered expected or unexpected.

Any change of condition or other follow-up information will be emailed to the Sponsor as soon as it is available or at least within 24 hours of the information becoming available. Events will be followed up until the event has resolved or a final outcome has been reached.

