9.4 Responsibilities

Chief Investigator/Clinical co-investigator :

Checking for AEs and ARs when participants attend for study visits.

- 1. Using medical judgement in assigning seriousness, causality and expectedness using the Reference Safety Information approved for the trial.
- 2. Using medical judgement in assigning seriousness and causality and providing an opinion on expectedness.
- 3. Ensuring that all SAEs and SARs (including SUSARs) are recorded and reported to the Sponsor within 24 hours of becoming aware of the event and provide further follow-up information as soon as available. Ensuring that SAEs and SARs (including SUSARs) are chased with Sponsor if a record of receipt is not received within 2 working days of initial reporting.
- 4. Ensuring that AEs and ARs are recorded and reported to the Sponsor in line with the requirements of the protocol.

Clinical co-investigator or independent clinical reviewer:

- 1. Clinical oversight of the safety of participants in the trial, including an ongoing review of the risk / benefit.
- 2. Using judgement in assigning seriousness, causality and expectedness of SAEs where it has not been possible to obtain local medical assessment.
- 3. Using judgement in assigning expectedness.
- 4. Immediate review of all SUSARs.
- 5. Review of specific SAEs and SARs in accordance with the trial risk assessment and protocol as detailed in the Trial Monitoring Plan.
- 6. Assigning Medical Dictionary for Regulatory Activities (MedDRA) or Body System coding to all SAEs and SARs.
- 7. Preparing the clinical sections and final sign off of the Development Safety Update Report (DSUR).

Sponsor:

- 1. Central data collection and verification of AEs, ARs, SAEs, SARs and SUSARs according to the trial protocol onto a MACRO database.
- 2. Reporting safety information to the CI, delegate or independent clinical reviewer for the ongoing assessment of the risk / benefit according to the Trial Monitoring Plan.

- 3. Reporting safety information to the independent oversight committees identified for the trial (Data Monitoring Committee (DMC) and / or Trial Steering Committee (TSC)) according to the Trial Monitoring Plan.
- 4. Expedited reporting of SUSARs to the MHRA and REC within required timelines.
- 5. Notifying Investigators of SUSARs that occur within the trial.
- 6. The unblinding of a participant for the purpose of expedited SUSAR reporting.

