9.8 Reporting urgent safety measures

If any urgent safety measures are taken the CI/Sponsor shall immediately and in any event no later than 3 days from the date the measures are taken, give written notice to the MHRA and the relevant REC of the measures taken and the circumstances giving rise to those measures.

9.9 The type and duration of the follow-up of subjects after adverse events.

Treatment will be stopped if a subject develops an unexpected reaction thought to be due to melatonin administration and will be followed up for 24h after the last melatonin dose. Any SUSAR related to the IMP will need to be reported to the Sponsor irrespective of how long after

IMP administration the reaction has occurred. Adverse events and reactions will be recorded for 14d after the last dose of the IMP.

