10.7 Subject population

The study population will be nurses and junior doctors (males and females) who are undertaking 2 series of night shifts within a 4-6 week period.

We will analyse on the basis of

- $\circ~$ All-randomized population: Any subject randomized into the study, regardless of whether they received study drug and whether they completed both arms of the study
- All-treated population: Any subject randomized into the study who received at least one dose of study drug

• Protocol-compliant population: Any subject who was randomized and received the protocol required study drug exposure and required protocol processing

When considering analysis of adverse events we will compare the incidence during the melatonin arm to the placebo arm.

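### Adverse event recording ends at the last study visit in section 9.2 and the synopsis, but 14 days after the last dose in sections 9.3 and 9.9

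*Protocol*

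**What the plan says.** The protocol sets the end of safety recording in four places.

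- Section 9.2, covering every adverse event (AE) and serious adverse event (SAE): "All AEs and SAEs will be recorded from the time of study entry until the end of the last study visit".
- Synopsis, follow-up duration: "End of final study visit". This agrees with 9.2.
- Section 9.3, covering SAEs and SUSARs only: events "occurring from the time of written informed consent until 14 days post cessation of trial treatment".
- Section 9.9: "Adverse events and reactions will be recorded for 14d after the last dose of the IMP". The same section lifts the limit for one class of event: "Any SUSAR related to the IMP will need to be reported to the Sponsor irrespective of how long after" dosing it occurred.

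On how events are found, section 9.4 lists "Checking for AEs and ARs when participants attend for study visits" as an investigator duty. Table 1 applies to both series, and its last scheduled assessments are before the fourth shift. Only the post-trial questionnaire and the optional focus group come later.

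On use of the data, section 10.7 says that for adverse events "we will compare the incidence during the melatonin arm to the placebo arm".

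**The concern.** For ordinary AEs, 9.2 and 9.9 cannot both govern. For SAEs, neither can 9.2 and 9.3. Staff who follow 9.2 and the synopsis would close the safety record within a day of the final dose, while other sections promise two further weeks. The visit schedule supports the shorter rule, because checking is tied to visits and no visit follows the fourth-shift assessment of series 2. The questionnaire does not fill the gap: its one side-effect item (section 16.11) is an undated agreement scale that is not linked to a treatment period.

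The crossover adds a second problem. Two dosing series lie 4–6 weeks apart, and neither 9.3 nor 9.9 says whether the 14 days run after each series or only after the last dose of the trial. Events in the gap might or might not count to the preceding treatment. Depending on the answer, the two periods are observed for very different lengths of time, and the incidences compared under 10.7 would not rest on a common window.

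**Working it through.** **Inputs from the protocol**

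- Doses: three per series, one after each of shifts 1–3 (section 8.6, Table 1).
- Last visit of a series: before shift 4 (Table 1).
- Gap between series: about 4–6 weeks, taken as 28–42 days (section 6.1).
- Recording after the last dose: to the last visit (9.2) or 14 days (9.3, 9.9).
- Sequence: 1:1 in blocks of 8 (section 7.3); 32 randomised, 25 completers (section 3.3). The 32 reproduces: 25 / (1 − 0.20) = 31.25, rounded up to 32. Here it serves only to set the sequence splits.

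**Assumption.** The protocol gives no clock times. Doses are placed at 09:00 on Days 2, 3 and 4, and the last visit at 20:00 on Day 4. Moving these by a few hours does not change the conclusion.

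**Step 1: size of the conflict after the final dose**

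- Under 9.2: 09:00 to 20:00 = 11 h = 0.46 day.
- Under 9.3 or 9.9: 14 days.
- Difference: 14 − 0.46 ≈ 13.5 days.

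**Step 2: capture per period, counted from the first dose of that period**

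Period 2 under 9.2 is 2 days (dose 1 to dose 3) + 0.46 = 2.46 days. With 14 days after the last dose it is 2 + 14 = 16 days. If gap events count to the preceding treatment, period 1 lasts until the first dose of period 2, that is 28–42 days.

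| Reading | Period 1 | Period 2 | Ratio |
|---|---|---|---|
| 9.2 governs, gap events count to period 1 | 28–42 d | 2.46 d | 11.4–17.1 |
| 9.9, last dose = final dose of the trial, gap events count to period 1 | 28–42 d | 16 d | 1.75–2.6 |
| 14 days after the last dose of each series | 16 d | 16 d | 1 |

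The 16-day window ends before series 2 begins, even with a 28-day gap.

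**Step 3: effect on the treatment comparison, first reading, participants with both periods**

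With *a* participants melatonin-first, *b* placebo-first and gap *g*:

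- melatonin days = *a·g* + *b*·2.46
- placebo days = *b·g* + *a*·2.46

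Results:

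- 16/16: equal, ratio 1.0.
- 13/12, *g* = 28: 393.5 / 368.0 = 1.07. With *g* = 42: 575.5 / 536.0 = 1.07.
- 14/11: 1.22 (*g* = 28) and 1.24 (*g* = 42).
- 16/9, *g* = 28: 470.1 / 291.3 = 1.61. With *g* = 42: 694.1 / 417.3 = 1.66.

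**The case against.** Much can be said for the plan.

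- **There are two end points, not three.** Sections 9.3 and 9.9 agree on 14 days, and 9.3 covers only SAEs and SUSARs. This stands. The conflict for ordinary AEs is 9.2 against 9.9, and for SAEs it is 9.2 against 9.3.
- **A reader might infer that nothing is recorded after the last series.** That is true only if 9.2 overrides the other sections, and the protocol does not say that it does. SUSARs have no time limit in any case.
- **A reader might infer a 50- to 75-fold imbalance.** Counting only time after the last dose gives (28 − 3.5)/0.5 = 49 to (42 − 3.5)/0.5 = 77. This needs 9.2 to govern and every gap event to be assigned to period 1. The wording of 10.7 can equally be read as covering only events during each series, which gives equal periods.
- **A reader might infer that the treatment comparison is biased by order.** The imbalance is between periods. Order is randomised 1:1, so each treatment comes first equally often.
- **A reader might infer that someone who stops after series 1 adds weeks of follow-up to one arm.** On the plain reading of 9.2 that person's last visit lies in series 1, so recording stops there. Such a person loses the long gap.
- **Assigning events to arms is often left to the SAP, and late events may be few.** The SAP is not shown, section 9.7 expects clearance within 12 h, and the primary endpoint is feasibility. This limits the consequences and is why no detailed attribution rule is asked for here. It does not remove the contradiction about when recording ends, which belongs to the protocol.

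**Conclusion.** The contradiction holds. The synopsis and 9.2 end AE and SAE recording about half a day after the final dose, while 9.9 (AEs) and 9.3 (SAEs and SUSARs) run to 14 days. Following 9.2 as written would lose about 13.5 days of capture that other sections promise, and no described procedure would collect dated AEs in that time after series 2.

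The inequality between periods is conditional. It is about 11–17 to 1 if 9.2 governs and gap events count to the preceding treatment, 1.75–2.6 to 1 if 9.9 means the final dose of the trial, and absent if the window follows each series. Bias between melatonin and placebo arises only with unequal completion by sequence. It is small at 13/12 (about 1.07) and material only at a lopsided split such as 16/9 (1.6–1.7), which is hypothetical.

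These figures rest on the assumed clock times and on a gap of 28–42 days. The existence of the conflict does not depend on the exact times.

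**What to change.** 1. Reconcile the synopsis follow-up line and sections 9.2, 9.3 and 9.9 to a single recording end date, stated as the same length after the last dose of each series. The 14 days already in 9.3 and 9.9 would fit inside the gap without overlap. The sponsor should choose the length. The unlimited SUSAR reporting in 9.9 can stay as a separate statement.
2. If the chosen window extends beyond the last visit, add a brief contact at its end after series 2 to ask about adverse events. Text messages are already used as reminders (section 10.8).
3. State in 10.7 that the comparison of incidence uses these equal per-series windows. Further detail on analysis can be left to the SAP.

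The cost is a change of wording in five places and one short extra contact per participant.

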9.3 Recording and reporting of SAEs AND SUSARs

All SAEs / SUSARs occurring from the time of written informed consent until 14 days post cessation of trial treatment will be recorded on the SAE / SUSAR report form and faxed to the Sponsor within 24 hours of the research staff becoming aware of the event. Once all resulting queries have been resolved, the Sponsor will request the original form should also be posted to the Sponsor and a copy to be retained on site.

For each SAEs / SUSARs the following information will be collected:

- full details in medical terms and case description
- event duration (start and end dates, if applicable)
- action taken
- outcome
- seriousness criteria
- causality (i.e. relatedness to trial drug / investigation), in the opinion of the investigator
- whether the event would be considered expected or unexpected.

Any change of condition or other follow-up information will be emailed to the Sponsor as soon as it is available or at least within 24 hours of the information becoming available. Events will be followed up until the event has resolved or a final outcome has been reached.

9.4 Responsibilities

Chief Investigator/Clinical co-investigator :

Checking for AEs and ARs when participants attend for study visits.

- 1. Using medical judgement in assigning seriousness, causality and expectedness using the Reference Safety Information approved for the trial.
- 2. Using medical judgement in assigning seriousness and causality and providing an opinion on expectedness.
- 3. Ensuring that all SAEs and SARs (including SUSARs) are recorded and reported to the Sponsor within 24 hours of becoming aware of the event and provide further follow-up information as soon as available. Ensuring that SAEs and SARs (including SUSARs) are chased with Sponsor if a record of receipt is not received within 2 working days of initial reporting.
- 4. Ensuring that AEs and ARs are recorded and reported to the Sponsor in line with the requirements of the protocol.

Clinical co-investigator or independent clinical reviewer:

- 1. Clinical oversight of the safety of participants in the trial, including an ongoing review of the risk / benefit.
- 2. Using judgement in assigning seriousness, causality and expectedness of SAEs where it has not been possible to obtain local medical assessment.
- 3. Using judgement in assigning expectedness.
- 4. Immediate review of all SUSARs.
- 5. Review of specific SAEs and SARs in accordance with the trial risk assessment and protocol as detailed in the Trial Monitoring Plan.
- 6. Assigning Medical Dictionary for Regulatory Activities (MedDRA) or Body System coding to all SAEs and SARs.
- 7. Preparing the clinical sections and final sign off of the Development Safety Update Report (DSUR).

Sponsor:

- 1. Central data collection and verification of AEs, ARs, SAEs, SARs and SUSARs according to the trial protocol onto a MACRO database.
- 2. Reporting safety information to the CI, delegate or independent clinical reviewer for the ongoing assessment of the risk / benefit according to the Trial Monitoring Plan.

- 3. Reporting safety information to the independent oversight committees identified for the trial (Data Monitoring Committee (DMC) and / or Trial Steering Committee (TSC)) according to the Trial Monitoring Plan.
- 4. Expedited reporting of SUSARs to the MHRA and REC within required timelines.
- 5. Notifying Investigators of SUSARs that occur within the trial.
- 6. The unblinding of a participant for the purpose of expedited SUSAR reporting.
- 7. Checking for and notifying PIs of updates to the Reference Safety Information for the trial.
- 8. Preparing standard tables and other relevant information for the DSUR in collaboration with the CI and ensuring timely submission to the MHRA and REC.

Trial Steering Committee (TSC):

In accordance with the Trial Terms of Reference for the TSC, periodically reviewing safety data and liaising with the DMC regarding safety issues. See Appendix 1.

Data Monitoring Committee (DMC):

In accordance with the Trial Terms of Reference for the DMC, periodically reviewing overall safety data to determine patterns and trends of events, or to identify safety issues, which would not be apparent on an individual case basis. See Appendix 2.

9.5 Notification of deaths

Any deaths will be reported immediately to the sponsor irrespective of whether the death is thought to be related to the IMP, or an unrelated event.

9.6 Pregnancy reporting

Pregnant subjects or those trying to get pregnant will be excluded from participation but if a volunteer becomes pregnant during the course of their involvement with the trial then they will be followed (with their permission) to term.

9.7 Overdose

Several cases of overdose of Circadin have been reported post-marketing. Somnolence was the most reported adverse event. Most were mild to moderate in severity. Circadin has been administered at similar daily doses to that proposed here in clinical trials over 12 months without significantly changing the nature of the adverse reactions reported.

If a higher dose than intended is taken, which is highly unlikely, given the trial subjects, the maximum dose they would be able take if they took all their allocated tablets would be 9 x 2mg. We have reported previously that even doses of 100mg melatonin resulted in no adverse events other than mild transient drowsiness. Administration of daily doses of up to 300 mg of melatonin without causing clinically significant adverse reactions have been reported in the literature. If overdose occurs, drowsiness is to be expected. Clearance of the active substance is expected within 12h after ingestion. No special treatment is required. Any subject in whom an overdose occurred would therefore simply be monitored carefully for 24h after overdosing and an adverse event recorded.

